12.9. Columbia-Suicide Severity Rating Scale (C-SSRS)

The Columbia-Suicide Severity Rating Scale (C-SSRS) is a questionnaire used for suicide assessment that evaluates suicidal ideation and behavior.

This study will utilize the “Since Last Visit” version of the C-SSRS at each visit.

Subjects will be placed into categories for suicidal ideation and for suicidal behavior based on their responses to various questions.

The Suicidal Ideation categories will be determined as follows by examining the response to the 5 questions under Suicidal Ideation.

Type	Section
Suicidal Ideation	
(0) None - if response is No to Questions 1 and 2
 
(1) Wish to be Dead - if response to Question 1 is Yes and responses to Questions 2-5 are No.
 
(2) Non-Specific Active Suicidal Thoughts - if response to Question 2 is Yes and response to Questions 3-5 are No.
 
(3) Active Suicidal Ideation with Any Methods (Not Plan) without Intent to Act - if response to question 3 is Yes and response to questions 4 and 5 are No.
 
(4) Active Suicidal Ideation with Some Intent to Act, without Specific Plan - if response to Question 4 is Yes and response to Question 5 is No.
 
(5) Active Suicidal Ideation with Specific Plan and Intent - if response to Question 5 is Yes.

For suicidal behavior, the following categories will be used. The categories will be determined based on the response to the questions under Suicidal Behavior.

Type	Section
Suicidal Behavior	
 • Preparatory Acts or Behavior - if response to Preparatory Acts and Behavior is Yes and responses to Actual Attempt, Interrupted Attempt, and Aborted Attempt are No • Aborted Attempt - if response to Aborted Attempt is Yes and responses to Actual Attempt and Interrupted Attempt are No. • Interrupted Attempt - if response to Interrupted Attempt is Yes and response to Actual Attempt is No. • Actual Attempt - if response to Actual Attempt is Yes. • None - if responses to all the above 4 questions are No.

The frequency and percentage by DB treatment and overall, and visit will be summarized for all C-SSRS responses.

Frequency and severity of suicidality using the C-SSRS will be summarized, using a shift table to examine changes in C-SSRS Scores from baseline compared to the worst (highest) category during the treatment period and visit, by DB treatment and overall.

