6. GENERAL ASPECTS FOR STATISTICAL ANALYSIS

6.1. GENERAL METHODS

- All analyses and summaries will be produced using SAS[®] version 9.3 (or higher) for windows.
- All statistical summaries will be presented based on the treatment received in the double-blind core study (SEP360-202), called DB treatment. Because the treatment received in SEP360-310 is flexible, the treatment groups for summary in SEP360-310 will be labeled as:
 - placebo / dasotraline flexible,
 - dasotraline 2 mg/day / dasotraline flexible,
 - dasotraline 4 mg/day / dasotraline flexible,
 - dasotraline combined / dasotraline flexible, and
 - total.
- The dasotraline combined group will include those subjects who were treated in SEP360-202 with dasotraline 2 mg/day and dasotraline 4 mg/day.
- Summaries will also be presented by visits (Double-Blind Baseline, Open-Label Baseline, Weeks 1, 2, 4, 6, 10, 14, 18, 22, 26, Week 26 or Treatment Period LOCF,

and EOS). See the details for the DESS and PWC for discussion of the display of visits for those summaries.

- Unless otherwise specified, continuous variables will be summarized with descriptive statistics including: n, arithmetic mean, standard deviation (SD), 95% confidence interval for the mean, median, minimum, and maximum values. All categorical/qualitative data will be presented using frequency counts and percentages. Shift tables will be produced for some assessments and will contain counts and percentages of subjects in each cross-classification level of baseline versus post-baseline assessment. Only subjects with a non-missing value for both baseline and post-baseline, at a given visit, will be included in these tables.
- The listings will be provided using the enrolled population (defined in [Section 8.1](#)). For listings related to analyses conducted using the intent-to-treat population, a flag will be shown in the subject column identifying subjects who were excluded from the intent-to-treat population. In general, the subject listings will be sorted by the treatment group, subject number and assessment date (and time, if applicable).

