6.2.3. Missing Data and Last Observation Carried Forward (LOCF)

Methods for handling missing item responses on the questionnaire instruments (i.e. ADHD-RS-IV HV, Conners 3-P, and WFIRS-P) are described in different sections later on.

If a subject discontinues the study prematurely, the last available data (excluding early termination visit assessments if done more than 3 days after the last dose of study medication, unscheduled assessments after the early termination assessment if done more than 3 days after the last dose of study medication, and Withdrawal Period assessments) will be carried forward to the study endpoint (i.e. the LOCF approach) at Week 26. Visits earlier than the early termination date for subjects who discontinued the study prematurely will be included in the LOCF process, even if they are more than 3 days after the last dose of study medication.

The AE and concomitant medication start/end dates will be imputed based on the rules described in [Appendix 3](#).

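### The C-SSRS ideation categories in SAP 12.9 overlap for some complete answers and leave gaps if follow-up questions are blank

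*SAP*

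**What the plan says.** SAP 12.9 derives an ideation category from five questions. The rules are:

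- Category 0: "None - if response is No to Questions 1 and 2".
- Category 1: "Wish to be Dead - if response to Question 1 is Yes and responses to Questions 2-5 are No".
- Category 2: "Non-Specific Active Suicidal Thoughts - if response to Question 2 is Yes and response to Questions 3-5 are No".
- Category 3: "if response to question 3 is Yes and response to questions 4 and 5 are No".
- Category 4: "if response to Question 4 is Yes and response to Question 5 is No".
- Category 5: "Active Suicidal Ideation with Specific Plan and Intent - if response to Question 5 is Yes".

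The category feeds a shift table from baseline to the worst category on treatment, and by visit. SAP 12.9 also tabulates every C-SSRS response by visit, and SAP 12 lists all safety data for all enrolled subjects.

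For shift tables in general, SAP 6.1 states: "Only subjects with a non-missing value for both baseline and post-baseline, at a given visit, will be included in these tables".

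On incomplete forms, SAP 6.2.3 refers to "Methods for handling missing item responses on the questionnaire instruments (i.e. ADHD-RS-IV HV, Conners 3-P, and WFIRS-P", which leaves out the C-SSRS. The CSHQ and the PWC have their own missing-item rules in SAP 12.10 and 12.12. Section 12.9 has none.

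**The concern.** A severity classification should give every assessable form exactly one category. Here None looks at two questions, while categories 1 and 2 also need a No on each of Questions 3 to 5. The two kinds of rule do not fit together. None can be met while a more severe category is also met, and a positive answer to Question 1 or 2 can meet no category if the later items are empty.

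The frequency and severity of suicidal ideation is a named secondary endpoint (Protocol 6.2, SAP 5.2) in a paediatric safety study. Exclusion criterion 2 in Protocol 8.2 concerns only ideation items 4 and 5, so it does not keep out children whose only Yes is to Question 1 or 2. The milder positive categories can therefore be populated from baseline onward. At stake is whether the derived category, and the shift table built on it, reports them correctly.

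**Working it through.** The plan gives no figure to reproduce. The check applies the six rules literally to every possible answer pattern.

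**Complete answers.** Five Yes/No questions give 2^5 = 32 patterns. Patterns meeting each rule:

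- Category 5 (Q5 Yes): 2^4 = 16
- Category 4 (Q4 Yes, Q5 No): 2^3 = 8
- Category 3 (Q3 Yes, Q4 and Q5 No): 2^2 = 4
- Category 2 (Q2 Yes, Q3 to Q5 No): 2
- Category 1 (Q1 Yes, Q2 to Q5 No): 1
- None (Q1 and Q2 No): 2^3 = 8

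The sum is 16 + 8 + 4 + 2 + 1 + 8 = 39 assignments for 32 patterns. No pattern is without a category, and 39 − 32 = 7 are assigned twice. These are Q1 No and Q2 No with at least one Yes on Q3 to Q5 (2^3 − 1 = 7). Four of them also meet category 5, two category 4 and one category 3. The other 25 patterns get exactly one category.

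**Questions 3 to 5 blank.** A blank is not a No when the rules are read literally:

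| Q1 | Q2 | Rule met |
|---|---|---|
| No | No | None |
| Yes | No | no rule met |
| Yes | Yes | no rule met |
| No | Yes | no rule met |

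Only the negative pattern is classified. Categories 3 and 4 have the same form, since each needs a recorded No on the items above it.

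**Comparison within the same section.** For suicidal behaviour, None requires a No on all four questions and each category requires a No on those ranked above it. Of the 2^4 = 16 patterns, Actual Attempt takes 8, Interrupted 4, Aborted 2, Preparatory 1 and None 1, which sums to 16. With complete answers that scheme has no overlap, so the ideation None rule is the odd one out.

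**Effect on the shift table, if blanks occur.** Protocol Table 2 schedules the C-SSRS at nine on-treatment visits (2E to 10E). Suppose a child is uncategorised at one visit and None at the other eight. The worst available category is None, so the child stays in the table with an understated result. If instead the baseline category, or either side of a by-visit shift, is missing, SAP 6.1 drops the child from that comparison. For the OL baseline, SAP 6.2.1 uses Week 6 LOCF from the core study, so an uncategorised Week 6 form might instead be replaced by an earlier category. The SAP does not say whether LOCF is applied to items or to the derived category here.

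**The case against.** The strongest reply is that the gap may never arise. Neither document contains a skip instruction or says how an unasked item is stored. Protocol 11.3.6 says only that a trained rater gives the scale, and SAP 12.9 speaks of the responses to five questions, which suggests that five are recorded. The short None rule may be shorthand, since No to active suicidal thoughts would imply No to their more specific forms. All of this stands. A reader might infer that children whose only positive answer is a wish to be dead are in fact lost. The documents do not support that; it follows only if Questions 3 to 5 are stored blank.

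Two further inferences also go too far:

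- **That such a child is removed from the shift table.** For the worst-category comparison, the other visits normally keep the child in, and the risk is understatement.
- **That ideation is under-reported throughout, always in one direction.** A Yes to Question 1 still appears in the by-visit table of responses and in the listings. An uncategorised positive baseline would also hide an improvement.

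The reply does not meet two points. The overlap between None and categories 3 to 5 needs no assumption about blanks. The absence of any C-SSRS missing-item rule is also plain from the text.

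**Conclusion.** The ideation categories are not mutually exclusive as written: 7 of 32 complete patterns fall in two categories with no stated precedence. This is a count of patterns, not of children. The seven are internally inconsistent answer sets and may be rare, but each one sets None against a serious category.

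The categories are also not exhaustive if Questions 3 to 5 can be blank. The size of that second fault depends on a fact the documents do not give. If all five answers are always recorded, no assessment is affected. If Questions 3 to 5 are left blank whenever Question 2 is No, every assessment with Question 1 Yes and Question 2 No is uncategorised. The documents give no expected rate of ideation, so a number of children cannot be calculated.

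Either fault reaches only the derived category and the shift table, not the item-level results. It merits correction because it concerns a stated derivation rule for a named secondary safety endpoint.

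**What to change.** Replace the ideation rules in SAP 12.9 with these:

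1. Assign each assessment the highest-numbered ideation question answered Yes.
2. Assign None only when Questions 1 and 2 are both No and none of Questions 3 to 5 is Yes.
3. Treat a blank on Questions 3 to 5 as No only when Question 2 is No.
4. When Question 2 is Yes and any of Questions 3 to 5 is blank, keep the subject in at least category 2 and flag or query the blank.

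Under these rules all 32 complete patterns receive exactly one category, equal to the highest category met under the present rules. With Questions 3 to 5 blank, Q1 Yes/Q2 No becomes category 1, and Q2 Yes becomes category 2 with a flag.

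The cost is a few lines of SAP text and a small programming change, with no new data. Consistent, complete answers are classified as before. One cost should be acknowledged: rule 3 cannot tell a deliberate skip from an incomplete form. That is why it is confined to Question 2 No, and the sponsor should check against the CRF how unasked items are stored before finalising the wording.

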12.10. CHILDREN'S SLEEP HABITS QUESTIONNAIRE (CSHQ)

The CSHQ is a retrospective, 45-item parent questionnaire that is used to examine sleep behavior in young children. The questionnaire is completed at each clinical assessment by the subject's parent or guardian. Each scored question is rated on a 3-point scale as occurring "usually" (i.e., 5-7 times within the past week), "sometimes" (i.e., 2-4 times within the past week), or "rarely" (i.e., never or 1 time within the past week). A number of items on the questionnaire are reverse-scored, so that higher scores

consistently indicate problem behaviors. Ratings are combined to form eight subscales: Bedtime Resistance, Sleep Onset Delay, Sleep Duration, Sleep Anxiety, Night Wakings, Parasomnias, Sleep Disordered Breathing, and Daytime Sleepiness.

The CSHQ will be completed at Open-Label Baseline, and at each scheduled visit through Week 26 or ET.

The questions associated with each subscales are as follows:

Subscale	Question (Item Number)	Reverse Scored
Bedtime Resistance	Child goes to bed at the same time at night (R) (1)	Yes
	Child falls asleep alone in own bed (R) (3)	Yes
	Child falls asleep in parent's or sibling's bed (4)	No
	Child needs parent in the room to fall asleep (5)	No
	Child struggles at bedtime (cries, refuses to stay in bed, etc.) (6)	No
	Child is afraid of sleep alone (8)	No
Sleep Onset Delay	Child falls asleep within 20 minutes after going to bed (R) (2)	Yes
Sleep duration	Child sleeps too little (9)	No
	Child sleeps the right amount (R) (10)	Yes
	Child sleeps about the same amount each day (R) (11)	Yes
Sleep Anxiety	Child needs parent in the room to fall asleep (5)	No
	Child is afraid of sleeping in the dark (7)	No
	Child is afraid of sleep alone (8)	No
	Child has trouble sleeping away from home (visiting relatives, vacation, etc.) (21)	No

Subscale	Question (Item Number)	Reverse Scored
Night Wakings	Child moves to someone else's bed during the night (parent, brother, sister, etc.) (16)	No
	Child awakes once during the night (24)	No
	Child awakes more than once during the night (25)	No
Parasomnias	Child wets the bed at night (12)	No
	Child talks during sleep (13)	No
	Child is restless and moves a lot during sleep (14)	No
	Child sleepwalks during the night (15)	No
	Child grinds teeth during sleep (your dentist may have told you this) (17)	No
	Child awakens during night screaming, sweating, and inconsolable (22)	No
	Child awakens alarmed by a frightening dream (23)	No
Sleep Disordered Breathing	Child snores loudly (18)	No
	Child seems to stop breathing during sleep (19)	No
	Child snorts and/or gasps during sleep (20)	No
Daytime Sleepiness	Child wakes up by him/herself (26) (R)	Yes
	Child wakes up in negative mood (27)	No
	Adults or siblings wake up child (28)	No
	Child has difficulty getting out of bed in the morning (29)	No
	Child takes a long time to become alert in the morning (30)	No
	Child seems tired (31)	No
	Appeared very sleepy or fallen asleep Watching TV (32)	No
	Appeared very sleepy or fallen asleep Riding	No

Subscale	Question (Item Number)	Reverse Scored
	Car (33)	

A Total Sleep Disturbances score is calculated as the sum of all 33 CSHQ scored questions, and can range from 33 to 99. (Two scored items are counted twice in the calculation of two different subscales).

At any assessment, a missing response to an item associated with a subscale will result in that subscale set to missing. Any missing response to the 33 CSHQ questions will result in a missing Total Sleep Disturbances score.

Summaries of observed values and changes from DB baseline and OL baseline in observed values will be done by DB treatment and overall for each visit using descriptive statistics.

12.11. TANNER SCALE

The Tanner scale is a scale of physical development in children, adolescents, and adults. The scale defines physical measurements of development based on external primary and secondary sex characteristics, such as the size of the breasts, genitalia, testicular volume, and development of pubic and axillary hair.

The Tanner stage is collected for each subject at OL Baseline, and at the Week 26 or Early Termination visit.

A shift table comparing the baseline stage with the stage at Week 26 or Early Termination will be done by gender, DB treatment and overall. Percentages will be calculated using the number of subjects with an assessment completed at both baseline and EOS.

12.12. PHYSICIAN WITHDRAWAL CHECKLIST (PWC)

The Physician Withdrawal Checklist (PWC) is used to evaluate symptoms of withdrawal after discontinuation of study drug. Symptoms are assessed as present or absent and if present then intensity is assessed as mild, moderate, or severe.

This checklist will be assessed at the end of treatment visit (Week 26) or treatment termination and at the Week 29 or EOS Visit.

The scale includes 20 symptoms. Each symptom is assessed on a 4-point scale using the following:

- 0=Not Present
- 1=Mild
- 2=Moderate
- 3=Severe

The score for each question is summed to compute a total score ranging from 0 to 60. If the response to any question is missing, then the total score will be missing. The PWC will be summarized using descriptive statistics by visit for the total score. The number and percentage of subjects with a Present response (mild, moderate, or severe) will be provided for each of the 20 PWC items. In addition, responses of moderate or severe will be summarized separately at each visit.

Analyses of the PWC will be repeated by gender subgroups.

12.13. DISCONTINUATION-EMERGENT SIGNS AND SYMPTOMS (DESS) SCALE

The DESS Scale ([Rosenbaum-1998](#)) is a clinician-rated instrument of 43 items used to evaluate signs and symptoms associated with discontinuation or interruption of monoamine reuptake inhibitor treatment.

On non-clinic days, the DESS Scale will be completed by site staff during a call to the subject/parent/legal guardian.

The DESS will be assessed at the Week 26 or Early Termination Visit, and then reassessed at Week 27, Week 28, and Week 29 or End of Study.

Each of the 43 signs and symptoms is assessed and placed in one of the following categories: new symptom, old symptom but worse, old symptom but improved, old symptom but unchanged, and symptom not present. Each sign and symptom that is placed in the category new symptom or in the category old symptom but worse receives 1 point. All other categories receive 0 points. The total DESS score is the sum of the number of points, which corresponds to the number of symptoms rated as either a new symptom or as an old symptom but worse. The score ranges from 0 to 43, where higher scores indicate more discontinuation-emergent signs and symptoms. The total score and change from Week 26 will be summarized descriptively separately by visit. For each

symptom, the number and percentage of subjects reporting the symptom as new or worsened will be provided.

Analyses of the DESS will be repeated by gender subgroups.

13. STATISTICS (TO BE INCORPORATED INTO SECTION 16.1.9 OF CSR)

13.1. STATISTICAL METHODS AND ANALYSIS OUTPUTS

13.1.1. Statistical Methods

Statistical Analysis System (SAS) version 9.3 will be used to perform all the statistical analyses in the CSR.

14. QUALITY CONTROL

SAS programs are developed to produce clinical trial output such as analysis data sets, summary tables, data listings and figures. INC Research SOPs 03.010.02 and 03.013.02 provide an overview of the development of such SAS programs.

INC Research SOP 03.009.04 describes the quality control procedures that are performed for all SAS programs and output. Quality control is defined here as the operational techniques and activities undertaken to verify that the SAS programs produce the proper clinical trial output by checking for their logic, efficiency, and commenting, and by review of the produced output.

15. TABLE AND LISTING SHELLS

15.1. TABLE SHELLS: SEE ATTACHMENT 1

15.2. LISTING SHELLS: SEE ATTACHMENT 2

15.3. FIGURE SHELLS: SEE ATTACHMENT 3

17. APPENDIX 1 – SCHEDULE OF ASSESSMENTS

All assessments will be performed as per the “Schedule of Assessments” copied from the protocol.

	OL Baseline ^a	Treatment Period									Withdrawal Period		
Visit	1E	2E	3E	4E	5E	6E	7E	8E	9E	10E/ET	11E Call	12 E Call	13E/EOS
Week		Week 1	Week 2	Week 4	Week 6	Week 10	Week 14	Week 18	Week 22	Week 26 ^b	Week 27 ^b	Week 28 ^b	Week 29 ^b
Day	Day 0	Day 7 ± 3	Day 14 ± 3	Day 28 ± 3	Day 42 ± 3	Day 70 ± 3	Day 98 ± 3	Day 126 ± 3	Day 154 ± 3	Day 182 ± 3	Day 189 ± 3	Day 196 ± 3	Day 203 ± 3
Obtain informed consent/assent	X												
Inclusion/Exclusion criteria	X												
Dispense study drug ^c	X	X	X	X	X	X	X	X	X				
Study drug accountability		X	X	X	X	X	X	X	X	X			
Between visit contact ^d						At the approximate midpoint between Visits 5E and 6E, Visits 6E and 7E, Visits 7E and 8E, Visits 8E and 9E, and Visits 9E and 10E.							
Medical and Psychiatric History	X (carried over)												
Concomitant medication review	X (carried over)	X	X	X	X	X	X	X	X	X			X
Physical Examination	X (carried over)						X			X			X
Neurological Examination	X (carried over)						X			X			X
Height (measured by stadiometer)	X (carried over)	X	X	X	X	X	X	X	X	X			X
Weight (including body mass index)	X (carried over)	X	X	X	X	X	X	X	X	X			X
Vital Signs	X (carried over)	X	X	X	X	X	X	X	X	X			X
Electrocardiogram (ECG)	X (carried over)	X	X	X	X	X	X	X	X	X			X
Adverse Event Monitoring	X (carried over)	X	X	X	X	X	X	X	X	X			X

	OL Baseline ^a	Treatment Period									Withdrawal Period		
Visit	1E	2E	3E	4E	5E	6E	7E	8E	9E	10E/ET	11E Call	12 E Call	13E/EOS
Week		Week 1	Week 2	Week 4	Week 6	Week 10	Week 14	Week 18	Week 22	Week 26 ^b	Week 27 ^b	Week 28 ^b	Week 29 ^b
Day	Day 0	Day 7 ± 3	Day 14 ± 3	Day 28 ± 3	Day 42 ± 3	Day 70 ± 3	Day 98 ± 3	Day 126 ± 3	Day 154 ± 3	Day 182 ± 3	Day 189 ± 3	Day 196 ± 3	Day 203 ± 3
Tanner Staging	X (carried over)									X			
Columbia Suicide Severity Rating Scale (C-SSRS) Children's Assessment ^e	X (carried over)	X	X	X	X	X	X	X	X	X			X
Clinical Global Impression – Severity (CGI-S)	X (carried over)	X	X	X	X	X	X	X	X	X			
ADHD Rating Scale Version IV - Home Version (modified for investigator administration) (ADHD-RS-IV HV)	X (carried over)	X	X	X	X	X	X	X	X	X			
Conners 3rd Edition Parent (Conners 3-P)	X (carried over)	X	X	X	X	X	X	X	X	X			
Children's Sleep Habits Questionnaire (CSHQ)	X (carried over)	X	X	X	X	X	X	X	X	X			
Weiss Functional Impairment Rating Scale – Parent Report (WFIRS-P)	X (carried over)						X			X			
Physician Withdrawal Checklist (PWC) ^l										X			X
Discontinuation-Emergent Signs and Symptoms (DESS) Scale ^l										X	X	X	X
Hematology/Chemistry	X (carried over)						X			X			X
Thyroid panel ^f	X (carried over)						X			X			X
Lipid panel ^g	X (carried over)						X			X			X

	OL Baseline ^a	Treatment Period									Withdrawal Period		
Visit	1E	2E	3E	4E	5E	6E	7E	8E	9E	10E/ET	11E Call	12 E Call	13E/EOS
Week		Week 1	Week 2	Week 4	Week 6	Week 10	Week 14	Week 18	Week 22	Week 26 ^b	Week 27 ^b	Week 28 ^b	Week 29 ^b
Day	Day 0	Day 7 ± 3	Day 14 ± 3	Day 28 ± 3	Day 42 ± 3	Day 70 ± 3	Day 98 ± 3	Day 126 ± 3	Day 154 ± 3	Day 182 ± 3	Day 189 ± 3	Day 196 ± 3	Day 203 ± 3
Sex hormone tests ^h	X (carried over)						X			X			X
Serum β-hCG (in females) ⁱ	X (carried over)												X
Urinalysis	X (carried over)						X			X			X
Urine drug screen	X (carried over)		X		X	X	X	X	X	X			X
Urine β-hCG (in females) ⁱ					X	X	X	X	X	X			X
Breath alcohol test	X (carried over)						X						X

